10.2 Phase II Study Calendars

10.2.1 MK-3475 + MLA

	Screening	Surgical Resection/Debulking (OPTIONAL)	Day 1 (MLA) (no surgical resection / debulking) ¹⁵	Day 1 (MLA) (3 weeks post-surgical resection / debulking ¹⁶)	Day 2 to Day 9	Q3W ¹⁷	EOT ³
H&P, KPS	X				X ¹²	X	X
Brain MRI	X				X ²⁰	X ⁹	
CBC	X ¹⁸				X	X	
CMP ¹³	X ¹⁸				X	X	
INR, PT/PTT	X ¹⁸						
βhCG ¹¹	X ¹⁸				X ¹⁰		
TSH	X ¹⁸				X ²	X ²	
MK-3475					X ¹	X ⁴	
MLA			X ^{6, 15}	X ^{6, 16, 19}			
Surgical resection (optional)		X					
Biopsy			X ¹⁴				
Research blood		X ^{5,7}	X ^{5, 7}		X ⁵	X ⁵	X ⁵
Research lymph nodes		X ⁷	X ⁷			X ⁸	
Research tissue		X ⁷	X ⁷				
AE assessment	X						X ²¹

1. To begin no more than 1 week (+/- 3 days) after MLA or 3 weeks after surgery.
2. To be checked at the first MK-3475 dose and then every other dose thereafter
3. There will be one follow-up visit 4 weeks after EOT, and then patients will be followed for up to 2 years for survival
4. Patients currently on MK-3475 beyond the 2 year/35 cycle limit at the time of this amendment may remain on MK-3475 unless there is progression, toxicity or agreement by the patient and PI to come off therapy. The number of treatments is calculated starting with the first dose. Participants who stop the combination or MK-3475 after receiving 35 doses may be eligible for retreatment if they progress after stopping study intervention provided they meet the requirements detailed in Section 5.10. Participants may be retreated in the Second Course Phase (Retreatment) for up to an additional 17 cycles (approximately 1 year).
5. Refer to Section 9.1
6. Patients will receive peri- and post-operative care as per SOC. This typically includes treatment with steroids and anti-epileptics, repeated neurological exams (approx. hourly in the ICU and approx. every 2 hours in the step-down unit), and draws for CBC and CMP immediately post-MLA and again the following day.
7. At time of surgery
8. 6 weeks post-surgery only (+/- 1 week)
9. Every 9 weeks (+/- 1 week)
10. No more than 72 hours prior to the first dose only. Additional pregnancy tests are not required.
11. Women of childbearing potential only
12. One week +/- 2 days following MLA or on the first dose of MK-3475 (whichever comes first)
13. CMP consists of albumin, alk phos, ALT, AST, BUN, Ca++, Cl-, CO2, creatinine, glucose, K+, Na+, total bili, total protein.
14. For tissue diagnosis and immune monitoring. Biopsy is only for patients who did not have surgical resection and will be performed during MLA.
15. Applies only to patients who did not have surgical resection.
16. Applies only to patients who had surgical resection.
17. +/- 4 days
18. Within 2 weeks prior to registration.
19. MLA will take place at least 3 weeks but not more than 6 weeks after surgical resection/debulking.
20. An MRI should be collected and evaluated after any surgical procedure (MLA, surgical resection/debulking, or biopsy).
21. Adverse events will be followed for 30 days following last treatment. SAEs will be tracked for 90 days following the last dose of study treatment.

10.2.2 MK-3475 – MLA

This arm is not available to newly enrolled patients as of Amendment 12.

	Screening	Surgical Resection/ Debulking (OPTIONAL) ¹⁴	Biopsy Only ¹⁵	Cycle 1 Day 1 ¹¹	Q3W ¹⁶	EOT ³
H&P, KPS	X			X ¹¹	X	X
Brain MRI	X			X ¹⁸	X ⁸	
CBC	X ¹⁷			X	X	
CMP ¹²	X ¹⁷			X	X	
INR, PT/PTT	X ¹⁷					
βhCG ¹⁰	X ¹⁷			X ⁹		
TSH	X ¹⁷			X ²	X ²	
MK-3475				X ¹	X ⁴	
Surgical resection (optional)		X				
Biopsy			X ¹³			
Research blood		X ^{5,6}	X ^{5,6}	X ⁵	X ⁵	X ⁵
Research lymph nodes		X ⁶	X ⁶		X ⁷	
Research tissue		X ⁶	X ⁶			
AE assessment		X--			X ¹⁹	

1. To begin no more than 1 week (+/- 3 days) after biopsy (if applicable) or 3 weeks after surgery.
2. To be checked at the first MK-3475 dose and then every other dose thereafter
3. There will be one follow-up visit 4 weeks after EOT, and then patients will be followed for up to 2 years for survival
4. Treatment can continue for a maximum of 2 years/35 cycles after MLA. Patients currently on MK-3475 beyond the 2 year/35 cycle limit at the time of Amendment 13 may remain on MK-3475 unless there is progression, toxicity, or agreement by the patient and PI to discontinue treatment. Refer to Section 5.10 for guidance on whether a patient qualifies for re-treatment in the Second Course Phase and refer to Section 10.3 for the Second Course Phase calendar.
5. Refer to Section 9.1
6. At time of surgery
7. 6 weeks post-surgery only (+/- 1 week)
8. Every 9 weeks (+/- 1 week)
9. No more than 72 hours prior to the first dose only. Additional pregnancy tests are not required.
10. Women of childbearing potential only
11. One week +/- 2 days following biopsy or on the first dose of MK-3475 (whichever comes first). For patients who underwent surgical resection/debulking, MK-3475 will be started at least 3 weeks but not more than 6 weeks after surgery.
12. CMP consists of albumin, alk phos, ALT, AST, BUN, Ca++, Cl-, CO2, creatinine, glucose, K+, Na+, total bili, total protein.
13. For tissue diagnosis and immune monitoring. Biopsy is only for patients who did not have surgical resection and for patients in which the treating physician deems a biopsy clinically necessary.
14. Applies only to patients who had surgical resection.
15. Applies only to patients who did not have surgical resection.
16. +/- 4 days
17. Within 2 weeks prior to registration. As of amendment 12, patients will no longer be randomized in the Phase II portion of this trial. Phase II patients enrolled after the approval of amendment 12 will participate in a single treatment arm with MK-3475 and MLA and follow the schedule of events in section 10.2.1 of the protocol.
18. A standard of care MRI after the biopsy procedure is optional at the discretion of the treating neurosurgeon.
19. Adverse events will be followed for 30 days following last treatment. SAEs will be tracked for 90 days following the last dose of study treatment.

10.3 Second Course Phase Calendar

Day 1 of Second Course must start no more than 4 weeks after disease progression.

	Screening	Day 1	Q3W¹⁰	EOT⁸
H&P, KPS	X	X	X	X
Brain MRI	X		X ⁶	
CBC	X ³	X	X	
CMP ¹	X ³	X	X	
INR, PT/PTT	X ³			
βhCG ²	X ³	X ⁴		
TSH	X ³	X ⁵	X ⁵	
MK-3475		X	X ⁷	
AE assessment	X-----			X ⁹

1. CMP consists of albumin, alk phos, ALT, AST, BUN, Ca++, Cl-, CO2, creatinine, glucose, K+, Na+, total bili, total protein.
2. Women of childbearing potential only
3. Within 4 weeks of progression.
4. No more than 72 hours prior to the first dose only. Additional pregnancy tests are not required.
5. To be checked at the first MK-3475 dose and then every other dose thereafter
6. Every 9 weeks (+/- 1 week)
7. Participants may be retreated in the Second Course Phase (Retreatment) for up to an additional 17 cycles (approximately 1 year).
8. There will be one follow-up visit 4 weeks after EOT, and then patients will be followed for up to 2 years for survival
9. Adverse events will be followed for 30 days following last treatment. SAEs will be tracked for 90 days following the last dose of study treatment.
10. +/- 4 days

11.0 DATA SUBMISSION SCHEDULE

Case report forms with appropriate source documentation will be completed according to the schedule listed in this section.

Case Report Form	Submission Schedule
Original Consent Form	Prior to registration
Registration Form Eligibility Form Demographics Form Medical Record Number Form Participant Address Form On-Study Form On-Study Treatment History Form On-Study Surgical History Form	Prior to starting treatment
MK-3475 Dosing Form	With each dose of MK-3475 (during main study and second course as applicable)
MLA Form	Time of MLA
Surgery Form Treatment Assignment Form	Time of surgery
Research Nodes and Tissue Form (Phase II only)	Time of surgical procedure 6 weeks post-surgical procedure
Research Blood Form (Phase II only)	Prior to starting treatment Time of MLA Time of surgical procedure With each dose of MK-3475 (Per section 9.1)
Retreatment Form	Time of start of second course
Adverse Events Form	Continuous
Treatment Summary Form	Completion of treatment
Follow Up Form	Per protocol
Imaging Form	Baseline, every 9 +/- 1 weeks, and end of treatment
MedWatch Form	See Section 7.0 for reporting requirements

Any queries generated by Washington University must be responded to within 28 days of receipt by the participating site. The Washington University research team will conduct a regular review of data status at all secondary sites, with appropriate corrective action to be requested as needed.

11.1 Adverse Event Collection in the Case Report Forms

All adverse events that occur beginning with start of treatment (minus exceptions defined in Section 1.0) must be captured in the Toxicity Form. Baseline AEs should be captured on the Medical History Form.

Participant death due to disease progression should be reported on the Toxicity Form as grade 5 disease progression. If death is due to an AE (e.g. cardiac disorders: cardiac arrest),

report as a grade 5 event under that AE. Participant death must also be recorded on the Death Form.

12.0 MEASUREMENT OF EFFECT

12.1 Antitumor Effect – Solid Tumors

For the purposes of this study, patients should be re-evaluated for response every 9 +/- 1 weeks. In addition to a baseline scan, confirmatory scans should also be obtained 9 weeks (not less than 4) weeks following initial documentation of objective response.

Response and progression will be evaluated in this study using the updated response assessment criteria for high-grade gliomas: Response Assessment in Neuro-Oncology (RANO) working group guideline [JCO 28(11): 1963-1972, 2010].

Criteria for Determining First Progression Depending on Time from Initial Chemoradiotherapy

First Progression	Definition
Progressive disease < 12 weeks after completion of chemoradiotherapy	Progression can only be defined using diagnostic imaging if there is new enhancement outside of the radiation field (beyond the high-dose region or 80% isodose line) or if there is unequivocal evidence of viable tumor on histopathologic sampling (eg, solid tumor areas [ie, > 70% tumor cell nuclei in areas], high or progressive increase in MIB-1 proliferation index compared with prior biopsy, or evidence for histologic progression or increased anaplasia in tumor). Note: Given the difficulty of differentiating true progression from pseudoprogression, clinical decline alone, in the absence of radiographic or histologic confirmation of progression, will not be sufficient for definition of progressive disease in the first 12 weeks after completion of concurrent chemoradiotherapy.
Progressive disease \geq 12 weeks after chemoradiotherapy completion	

1. New contrast-enhancing lesion outside of radiation field on decreasing, stable, or increasing doses of corticosteroids.
2. Increase by $\geq 25\%$ in the sum of the products of perpendicular diameters between the first postradiotherapy scan, or a subsequent scan with smaller tumor size, and the scan at 12 weeks or later on stable or increasing doses of corticosteroids.
3. Clinical deterioration not attributable to concurrent medication or comorbid conditions is sufficient to declare progression on current treatment but not for entry onto a clinical trial for recurrence.
4. For patients receiving antiangiogenic therapy, significant increase in T2/FLAIR nonenhancing lesion may also be considered progressive disease. The increased T2/FLAIR must have occurred with the patient on stable or increasing doses of corticosteroids compared with baseline scan or best response after initiation of therapy and not be a result of comorbid events (eg, effects of radiation therapy, demyelination, ischemic injury, infection, seizures, postoperative changes, or other treatment effects).

Criteria for Response Assessment Incorporating MRI and Clinical Factors (Adapted from JCO 2010)

Response	Criteria
Complete response	
 Requires all of the following: complete disappearance of all enhancing measurable and nonmeasurable disease sustained for at least 4 weeks. No new lesions; stable or improved nonenhancing (T2/FLAIR) lesions. Patients must be off corticosteroids (or on physiologic replacement doses only) and stable or improved clinically. Note: Patients with nonmeasurable disease only cannot have a complete response; the best response possible is stable disease.
Partial response	
Requires all of the following:
 
 $\geq 50\%$ decrease compared with baseline in the sum of products of perpendicular diameters of all measurable enhancing lesions sustained for at least 4 weeks. No progression of nonmeasurable disease. Stable or improved nonenhancing (T2/FLAIR) lesions on same or lower dose of corticosteroids compared with baseline scan; the corticosteroid dose at the time of the scan evaluation should be no greater than the dose at time of baseline scan. Stable or improved clinically. Note: Patients with nonmeasurable disease only cannot have a partial response; the best response possible is stable disease.
Stable disease	
Requires all of the following:
 
 Does not qualify for complete response, partial response, or progression. Stable nonenhancing (T2/FLAIR) lesions on same or lower dose of corticosteroids compared with baseline scan. In the event that the corticosteroid dose was increased for new symptoms and signs without confirmation of disease progression on neuroimaging, and subsequent follow-up imaging shows that this increase in corticosteroids was required because of disease progression, the last scan considered to show stable disease will be the scan obtained when the corticosteroid dose was equivalent to the baseline dose.
Progression	
Defined by any of the following:
 
 $\geq 25\%$ increase in sum of the products of perpendicular diameters of enhancing lesions compared with the smallest tumor measurement obtained either at baseline (if no decrease) or best response, on stable or increasing doses of corticosteroids*. The absolute increase in any dimension must be at least 5mm when calculating the products. Significant increase in T2/FLAIR nonenhancing lesion on stable or increasing doses of corticosteroids compared with baseline scan or best response after initiation of therapy* not caused by comorbid events (e.g. radiation therapy, demyelination, ischemic injury, infection, seizures, postoperative changes, or other treatment effects).

Response	Criteria
	
 • Any new measureable lesion. • Clear clinical deterioration not attributable to other causes apart from the tumor (e.g. seizures, medication adverse effects, complications of therapy, cerebrovascular events, infection, and so on) or changes in corticosteroid dose. • Failure to return for evaluation as a result of death or deteriorating condition; or clear progression of nonmeasurable disease.

- NOTE. All measurable and nonmeasurable lesions must be assessed using the same techniques as at baseline.
- Abbreviations: MRI, magnetic resonance imaging; FLAIR, fluid-attenuated inversion recovery.
- Stable doses of corticosteroids include patients not on corticosteroids.

12.2 Disease Parameters

Measurable disease: Bi-dimensionally measurable lesions with clearly defined margins by MRI scan of ≥ 10 mm. All tumor measurements must be recorded in millimeters (or decimal fractions of centimeters).

Non-measurable or evaluable disease: Uni-dimensionally measurable lesions or lesions with margins not clearly defined such as areas of T2/FLAIR signal abnormality or poorly defined enhancing abnormality.

Note: For cystic lesions, the only measurable part is any enhancement area around the cyst that is clearly defined and bi-dimensionally measurable. The cyst itself should not be considered measurable or non-measurable disease.

Target lesions: All measurable lesions that are seen at baseline MRI. Target lesions should be selected on the basis of their size (lesions with the longest diameter), but in addition should be those that lend themselves to reproducible repeated measurements. It may be the case that, on occasion, the largest lesion does not lend itself to reproducible measurement in which circumstance the next largest lesion, which can be measured reproducibly should be selected. When there are too many measurable lesions, choose the largest 3 lesions as target lesions to follow. The other measurable lesions should be considered evaluable for the purpose of objective status determination.

Non-target lesions: All non-measurable lesions should be identified as non-target lesions and should also be recorded at baseline. Measurements of these lesions are not required, but the presence, absence, or in rare cases unequivocal progression of each should be noted throughout follow-up.

12.3.1 Evaluation of Target Lesions

Complete Response (CR): Disappearance of all target lesions.

Partial Response (PR): $\geq 50\%$ decrease compared with baseline in the sum of products of perpendicular diameters of all target lesions sustained for at least 4 weeks.

Progressive Disease (PD): At least a 25% increase in the sum of products of perpendicular diameters of at least 1 target lesion, taking as reference the smallest sum of products of perpendicular diameters on study (this includes the baseline sum if that is the smallest on study). The absolute increase in any dimension must be at least 5mm when calculating the products of perpendicular diameters.

In the event of surgical intervention for clinical reasons of a radiographically progressing tumor when subsequent surgical pathology demonstrates a predominant immune-mediated reaction **with no obvious progression of tumor**, the subject will be deemed not progressed and allowed to resume study treatment as assigned prior to the surgery at a time deemed safe by the treating physician, but no later than 8 weeks from the surgery.

Stable Disease (SD): Neither sufficient shrinkage to qualify for PR nor sufficient increase to qualify for PD, taking as reference the smallest sum of products of perpendicular diameters while on study.

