12.3.2 Evaluation of Non-Target Lesions

Complete Response (CR): Disappearance of all non-target lesions.

Non-CR/Non-PD: Persistence of one or more non-target lesion(s).

Progressive Disease (PD): Appearance of one or more new lesions and/or unequivocal progression of existing non-target lesions on stable or increasing doses of corticosteroids compared with baseline scan or best response after initiation of therapy* not caused by comorbid events (e.g. radiation therapy, demyelination, ischemic injury, infection, seizures, postoperative changes, or other treatment effects). Unequivocal progression should not normally trump target lesion status. It must be representative of overall disease status change, not a single lesion increase.

Although a clear progression of “non-target” lesions only is exceptional, the opinion of the treating physician should prevail in such circumstances, and the progression status should be confirmed at a later time by the review panel (or Principal Investigator).

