12.3.3 Evaluation of Best Overall Response

The best overall response is the best response recorded from the start of the treatment until disease progression/recurrence (taking as reference for progressive disease the smallest measurements recorded since the treatment started). The patient's best response assignment will depend on the achievement of both measurement and confirmation criteria.

Summary of the RANO Response Criteria (Adapted from JCO 2010)

Criterion	CR	PR	SD	PD
T1 gadolinium enhancing disease	None	$\geq 50\% \downarrow$	$< 50\% \downarrow$ but $< 25\% \uparrow$	$\geq 25\% \uparrow^*$
T2/FLAIR	Stable or \downarrow	Stable or \downarrow	Stable or \downarrow	\uparrow^*
New lesion	None	None	None	Present*
Corticosteroids	None	Stable or \downarrow	Stable or \downarrow	NA†
Clinical status	Stable or \uparrow	Stable or \uparrow	Stable or \uparrow	\downarrow^*
Requirement for response	All	All	All	Any*

Abbreviations: RANO, Response Assessment in Neuro-Oncology; CR, complete response; PR, partial response; SD, stable disease; PD, progressive disease; FLAIR, fluid-attenuated inversion recovery; NA, not applicable.

* Progression occurs when this criterion is present.

† Increase in corticosteroids alone will not be taken into account in determining progression in the absence of persistent clinical deterioration.

NOTE: Patients may continue on treatment and remain under close observation and evaluation at 4-8 week intervals if there is uncertainty regarding whether pseudoprogression may be present as determined by the investigators. If subsequent radiographic or clinical assessments suggest that the patient is in fact experiencing progression, then the date of progression should be the time point at which this issue was first raised. Similarly, stable disease may be assigned in cases of presumed “pseudoprogression” associated with decreased steroid use.

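### The target-lesion progression rule in Section 12.3.1 does not match Section 12.1: it ties a sum to a single lesion and lacks the corticosteroid condition

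*Combined protocol and SAP*

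**What the plan says.** Section 12.1 names the standard: "Response and progression will be evaluated in this study using the updated response assessment criteria for high-grade gliomas", that is, RANO. Its enlargement criterion for progression is a rise of at least 25%, described as an "increase in sum of the products of perpendicular diameters of enhancing lesions compared with the smallest tumor measurement". That smallest measurement is the one at baseline or at "best response, on stable or increasing doses of corticosteroids". At least one dimension must also have grown by 5 mm.

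Section 12.3.1 restates the rule for target lesions. Progression is "At least a 25% increase in the sum of products of perpendicular diameters of at least 1 target lesion". The value to compare with is a total over lesions, since the rule continues by "taking as reference the smallest sum of products of perpendicular diameters on study". The same 5 mm minimum applies. No steroid condition follows. The partial-response rule in the same section refers to the "sum of products of perpendicular diameters of all target lesions sustained for at least 4 weeks".

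Section 12.3.2, on non-target lesions, does carry the steroid condition: "unequivocal progression of existing non-target lesions on stable or increasing doses of corticosteroids".

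The summary table in Section 12.3.3 marks corticosteroids as not applicable in the progression column, and its footnote concerns dose increases only. The note below the table adds a discretionary provision for pseudoprogression with reduced steroid use: "Similarly, stable disease may be assigned in cases of presumed" pseudoprogression. It also dates a progression that later assessments support back to when the question first arose.

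Section 12.3.6 counts progression as a PFS event, and Section 2.1 makes PFS the phase II primary objective.

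**The concern.** The rule in 12.3.1 has two faults. First, its two halves do not fit together. The increase is attached to as few as one lesion, but the reference is a sum over lesions. An assessor could compare one lesion with its own earlier size, the total with the earlier total, or one lesion with the earlier total. Second, it drops the steroid condition that 12.1 and 12.3.2 both carry. Enhancement that grows while steroids are being reduced would then count as target-lesion progression in 12.3.1, although it does not meet the enlargement criterion in 12.1.

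What is at stake is whether two assessors reading the same scan would record the same event for the primary endpoint. Section 16 describes a multicenter trial, so different people will apply this text.

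**Working it through.** The plan attaches no figure to this rule, so there is none to reproduce. The check compares the wording and then applies each reading to lesion sizes. **All lesion sizes are assumed for illustration**; the 25% and 5 mm thresholds come from 12.1 and 12.3.1.

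**1. The rules side by side**

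| Section | What is measured | Reference | Steroid condition |
|---|---|---|---|
| 12.1, progression | Sum over enhancing lesions | Smallest measurement | Stable or increasing dose |
| 12.3.1, progression | A sum of at least one target lesion | Smallest sum on study | None |
| 12.3.1, partial response | Sum over all target lesions | Baseline | None |
| 12.3.2, progression | Non-target lesions, judged unequivocally | Baseline or best response | Stable or increasing dose |

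**2. Two target lesions, steroid dose not reduced**

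Reference lesions are 30×30 mm and 15×15 mm. The reference sum is 900 + 225 = 1125 mm², and the 25% threshold on the sum is 1.25 × 1125 = 1406.25 mm².

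- *Reading A, one lesion against its own smallest product.* The threshold for the small lesion is 1.25 × 225 = 281.25 mm². At 20×15 mm it measures 300 mm² (300/225 − 1 = +33%, with +5 mm in one dimension), so this is progression. The sum has changed by (900 + 300)/1125 − 1 = +6.7%, so the 12.1 criterion is not met.
- *Reading B, sum against sum, as in 12.1.* With the large lesion unchanged, the small one must reach 1406.25 − 900 = 506.25 mm², that is 22.5×22.5 mm (sum +25%).
- *Reading C, one lesion against the summed reference.* One lesion alone must reach 1406.25 mm², that is 37.5×37.5 mm. The sum would by then have changed by (1406.25 + 225)/1125 − 1 = +45%. With the large lesion at 35×35 mm (1225 mm²), the sum has changed by (1225 + 225)/1125 − 1 = +28.9%. That is progression under 12.1 but not under C, because 1225 < 1406.25.

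Reading A can call progression earlier than 12.1, and Reading C later. With a single target lesion the three readings coincide, because the sum is that lesion.

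**3. One target lesion, steroid dose reduced**

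A lesion that goes from 20×20 to 25×20 mm changes by 500/400 − 1 = +25%, with +5 mm in one dimension. If the dose is lower than at the reference scan, this meets 12.3.1 but not the enlargement criterion in 12.1. This second route does not depend on the number of lesions.

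**4. Who could be affected**

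- *Two or more target lesions.* Section 12.2 follows up to three, but Section 3.2 (item 7) limits this group. Bilateral multifocal disease is excluded, apart from eligible corpus callosal tumors, and unilateral multifocal disease must be treatable in one laser procedure.
- *A scan on a lower steroid dose than the reference scan.* Section 5.3 describes perioperative steroids as typical, Section 6.0 tapers steroids given for immune-related events, and Section 5.7 permits bevacizumab for steroid sparing. A perioperative taper matters only if the reference scan was taken on the higher dose. Baseline imaging precedes ablation (12.3), and dexamethasone above 4 mg at registration is excluded (3.2, item 15). The route is therefore open mainly when a scan after a procedure became the reference.

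In both steps, another 12.1 criterion, such as a new lesion or clinical decline, could make the patient a progression under either section.

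**5. A separate text slip**

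In Section 12.3 the FDG-PET entry calls the scan an adjunct and then says it should be the main or only method. The parallel perfusion entry says the opposite. The word *not* has been lost. No effect on PFS is claimed from this.

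**The case against.** The strongest reply is that the correct rule is already in the protocol. Section 12.1 names RANO and gives the summed rule in full, with the steroid condition. The 12.3.1 reference is itself a sum, for stable disease as well as progression. Section 12.3.2, although written for non-target lesions, says that progression must reflect overall status and not growth of one lesion. This stands as evidence of intent. It does not make the 12.3.1 sentence coherent, and no section says that 12.1 prevails.

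A second reply is that the complete- and partial-response lines in 12.3.1 also omit the steroid and clinical conditions of 12.1, so 12.3.1 may be only the size component of a fuller assessment. This stands in part. Against it, 12.3.2 is a component rule of the same kind and does repeat the steroid condition for progression.

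A third reply points to the safeguards. Section 5.9 stops treatment on confirmed progression, and 12.3.3 allows observation when pseudoprogression is uncertain and stable disease when steroids have been reduced. These soften the effect on treatment. They protect the PFS date less well: the stable-disease provision is discretionary, and a progression supported later is dated back.

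A reader might go further and infer that PFS is biased, or that progression dates already recorded should be re-checked in patients with several lesions or a steroid reduction. The documents support neither. Reading A and Reading C pull in opposite directions, and nothing shows that any site used a single-lesion rule. A re-check of recorded dates would miss progression that Reading C had left unrecorded. The form list in Section 11 shows no form for steroid dose. Re-dating only selected patients in a single-arm trial could itself introduce bias.

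**Conclusion.** The target-lesion progression rule in 12.3.1 is wrong as written and conflicts with 12.1. The severity is minor. Followed literally, it can change a progression call in patients with two or more target lesions, or on a scan taken at a lower steroid dose than the reference scan. For a patient with one target lesion and no such reduction, the two sections agree on enlargement.

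The size is known only per scan and only for the assumed lesions: a call at +6.7% of the sum under one reading, and none until +45% under another when only the large lesion grows, where 12.1 would call at +25%. The share of patients in either group is not in the documents, so no effect on median PFS can be calculated and no direction is claimed. No sample-size or power figure changes. The summed RANO rule with the steroid condition is very probably what was meant.

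**What to change.** In the progression entry of Section 12.3.1, replace the reference to at least one lesion with *all target lesions*, as the partial-response entry already has it. Add the steroid condition in the wording of 12.1. State that the 12.1 criteria govern progression and the PFS date for all patients. Separately, insert *not* in the FDG-PET entry of Section 12.3.

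The cost is a few words in Section 12 and a note to sites. No new scans, readers or patients are needed, and no selective review of recorded progression dates is proposed.
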